1.3.2. Schedule of Activities – Follow-up Phase

After study intervention completion (or early discontinuation), all participants will enter the 48-week follow-up phase (unless they withdraw consent). Participants who could not stop NAs or who have re-started NA treatment during the follow-up period, provided that their HBV DNA and ALT values are stable, will have less frequent visits (at least every 12 weeks).

Phase	Follow-up ^{a,b}												
	FU W2	FU W4	FU W8	FU W12	FU W16	FU W20	FU W24	FU W28	FU W32	FU W36	FU W40	FU W44	FU W48 EOS
FU Study Day (Window)	15 (+/- 4d)	29 (+/- 4d)	57 (+/- 4d)	85 (+/- 4d)	113 (+/- 4d)	141 (+/- 4d)	169 (+/- 4d)	197 (+/- 4d)	225 (+/- 4d)	253 (+/- 4d)	281 (+/- 4d)	309 (+/- 4d)	337 (+/- 4d)
Visits in case all treatments including NA stopped	X	X	X	X	X	X	X	X	X	X	X	X	X
Visits in case NA is not stopped or NA re-started, provided that their HBV DNA and ALT values are stable				X			X		X				X
Study Intervention Administration													
Administer/Dispense NA, as applicable ^c	(X)	(X)	(X)	(X)	(X)	(X)	(X)	(X)	(X)	(X)	(X)	(X)	(X) ^v
NA accountability, as applicable	(X)	(X)	(X)	(X)	(X)	(X)	(X)	(X)	(X)	(X)	(X)	(X)	(X)
Assess NA re treatment criteria, as applicable	(X)	(X)	(X)	(X)	(X)	(X)	(X)	(X)	(X)	(X)	(X)	(X)	(X)
Safety Assessments													
Symptom directed physical examination, including body weight (if applicable)	X	X	X	X	X	X	X	X	X	X	X	X	X
Vital signs ^d	X	X	X	X	X	X	X	X	X	X	X	X	X
Triplectate 12 lead ECG ^e			X										
Liver ultrasound ^f								X					X
Clinical Laboratory Tests													
Hematology	X	X	X	X	X		X	X	X	X	X	X	X
Blood chemistry (including liver function tests) ^{g,h,i}	X	X	X ^j	X	X ^j	X ^j	X	X ^j	X ^j	X	X ^j	X ^j	X
Blood coagulation	X	X		X			X			X		X	X
Urinalysis ^k		X ^m	(X)	(X)	(X)	(X)	(X)	(X)	(X)	(X)	(X)	(X)	X
Urine chemistry ^l		X ^m	(X)	(X)	(X)	(X)	(X)	(X)	(X)	(X)	(X)	(X)	X
Urine pregnancy test (women of childbearing potential only)		X	X	X	X	X	X	X ⁿ	X				
Alpha fetoprotein ⁱ								X					X
Efficacy Assessments													
Fibroscan ^o								(X)					(X)
HBV Virology													
Blood sample collection for HBV DNA and HBV RNA ^{p,w}	X	X	X	X	X	X	X	X	X	X	X	X	X
Sampling for viral genome sequencing ^q		X		X		X		X	X	X	X	X	X

Phase	Follow-up ^{a,b}												
	FU W2	FU W4	FU W8	FU W12	FU W16	FU W20	FU W24	FU W28	FU W32	FU W36	FU W40	FU W44	FU W48 EOS
Follow up (FU) Week (W)	15 (+/- 4d)	29 (+/- 4d)	57 (+/- 4d)	85 (+/- 4d)	113 (+/- 4d)	141 (+/- 4d)	169 (+/- 4d)	197 (+/- 4d)	225 (+/- 4d)	253 (+/- 4d)	281 (+/- 4d)	309 (+/- 4d)	337 (+/- 4d)
FU Study Day (Window)													
Visits in case all treatments including NA stopped	X	X	X	X	X	X	X	X	X	X	X	X	X
Visits in case NA is not stopped or NA re-started, provided that their HBV DNA and ALT values are stable				X			X			X			X
HBV Serology													
Blood sample collection for:													
Anti HBs and anti Hbe		X		X			X			X			X
HBsAg and HBeAg (qualitative)				X			X						X
HBsAg (quantitative)	X	X	X	X	X	X	X	X	X	X	X	X	X
HBeAg (quantitative)	X	X	X	X	X	X	X	X	X	X	X	X	X
HBcrAg ^p		X		X			X			X			X
Exploratory serology ^r	X	X	X	X	X	X	X			X			X
Exploratory Host Biomarkers													
Whole blood RNA gene expression		X						X					X
Whole blood single cell profiling		X	X	X	X			X			X		X
Host serum proteins (eg, cytokines)		X	X	X	X			X			X		X
Antidrug antibodies (to JNJ 3989)				X			X						X
Immune Monitoring													
Immune cells (PBMCs) (selected sites only) ^s	X		X	X				X					X
Pharmacogenomics (Host DNA)													
Exploratory host genotyping and epigenetic research (optional) ^t	X			X				X					X
PRO Evaluations													
HBV specific self stigma				X				X			X		X
EQ 5D 5L				X				X			X		X
Ongoing Participant Review													
Concomitant therapy ^u	X	X	X	X	X	X	X	X	X	X	X	X	X
Adverse events ^u	X	X	X	X	X	X	X	X	X	X	X	X	X

General Note: The PRO assessments and ECGs should be completed before any tests, procedures or other consultations for that visit.

AFP: Alpha-fetoprotein; ALP: alkaline phosphatase; ALT: alanine aminotransferase; AST: aspartate aminotransferase; CKD-EPI: Chronic Kidney Disease Epidemiology Collaboration; d: days; DBP: diastolic blood pressure; DNA: deoxyribonucleic acid; ECG: electrocardiogram; eGFR: estimated glomerular filtration rate; EOS: end of study; EQ-5D-5L: 5-Level EuroQol 5-Dimension; FU: follow-up; HBcrAg: hepatitis B core-related antigen; HBe(Ag): hepatitis B e (antigen); HBs(Ag): hepatitis B surface (antigen); HBV: hepatitis B virus; HCC: hepatocellular carcinoma; ICF: informed consent form; ISA: intervention-specific appendix; NA: nucleos(t)ide analog; PBMC: peripheral blood mononuclear cells; PRO: patient-reported outcome; RNA: ribonucleic acid; SBP: systolic blood pressure; ULN: upper limit of normal; W: Week.

- a. All follow-up study visits are to be scheduled relative to the last dose of JNJ-3989/JNJ-6379/placebo. An unscheduled visit can be performed upon the investigator's discretion, in case of HBV DNA elevations, ALT elevations, other signs of worsening of liver disease, or for any other reason during follow-up.
- b. Participants who withdraw consent during follow-up will be offered an optional safety follow-up visit to occur on the day of consent withdrawal. For the optional safety follow-up visit, assessments are at the investigator's discretion and could be similar to the early WD visit.
- c. No JNJ-3989/JNJ-6379/placebo will be administered or dispensed during follow-up. Administration/Dispensation of NA is only applicable for participants who could not stop NA treatment at Week 48, or for those who met the NA re-treatment criteria. In between study visits, participants will take NA at home and they will bring their NA treatment with them to each study visit. At study visits, the NA treatment should be taken on site.
- d. Vital signs include supine SBP, DBP, pulse rate, and body temperature.
- e. All ECGs will be read centrally.
- f. A liver ultrasound is recommended every 6 months for HCC screening in high-risk populations (ie, participants with a family history of HCC, Asian males >40 years, Asian females >50 years; Africans and African Americans).
- g. Biochemistry samples must be taken after fasting for at least 10 hours for measurement of phosphate, calcium, creatinine, and lipids.
- h. Creatinine clearance (eGFR calculated by the CKD-EPI formula) will be assessed.
- i. ALT/AST elevations (ie, ALT and/or AST ≥ 3 ULN and ≥ 3 nadir [ie, lowest value during study participation]), should trigger an assessment of confounding factors (alcohol intake, change in concomitant medication, and comorbidities) and a confirmatory visit, to be scheduled preferably within 7 days of the receipt of the initial ALT/AST results, to repeat laboratory testing of AFP, ALT, AST, ALP, bilirubin (total and direct), INR albumin, and HBV DNA. Additional tests should be considered based on clinical judgement. For more details and further management guidance, refer to Section 8.3.6.3, Intervention-emergent ALT/AST Elevations and Section 10.6, Appendix 6, Intervention-emergent ALT/AST Elevations.
- j. Liver function tests only.
- k. Urinalysis by dipstick: specific gravity, pH, glucose, protein, blood, ketones, bilirubin, urobilinogen, nitrite, leukocyte esterase, and microscopic analysis if needed. The dipstick reading should be done as soon as possible and in accordance with the manufacturer's recommendation. In case of a positive dipstick result, a urine sample will be set aside for additional examination of the positive parameter at the central laboratory (eg, quantification as applicable).
- l. Urine chemistry sample (quantitative measurement): creatinine, sodium, phosphate, glucose, protein, and albumin.
- m. A urinalysis and urine chemistry sample will be taken at Follow-up Week 4. In case of abnormalities, the tests should be repeated at the following visits.
- n. Urine pregnancy tests will be provided to the participants for testing at home as urine pregnancy test should be done at least every 4 weeks. Results will be reported at the next visit. If urine pregnancy test is positive, the investigator needs to be informed immediately by the participant.
- o. Only applicable to participants who are enrolled at a site with an on-site Fibroscan device.
- p. HBcrAg and HBV RNA samples may be batched and only selected samples may be tested at the sponsor's request. Samples can be used for assessment of other serologic/virologic markers of HBV.
- q. Samples may be sequenced based on the sponsor virologist's request, considering the HBV DNA levels. A sample for viral genome sequencing will be taken at an unscheduled visit for confirmation of virologic relapse.
- r. Exploratory serology samples may be analyzed at the sponsor's discretion. Samples may be used to assess virologic or serologic markers of HBV.
- s. PBMC samples will be collected at selected sites only. Additional PBMC samples may be taken in case of ALT flares, upon discussion with the sponsor, and may require an unscheduled visit.

- t. These samples are optional and will only be collected from participants who consent separately to this component of the study.
- u. Adverse events and concomitant medications will be monitored from the time a signed and dated ISA ICF is obtained until completion of the participant's last ISA-related procedure.
- v. The investigator should consider to re-start NA treatment per local standard of care at the EOS visit (Follow-up Week 48) for participants who discontinued NA treatment at Week 48, who did not re-start NA treatment during the follow-up phase, and who did not achieve and maintain HBsAg seroclearance. NA will not be provided by the sponsor after the final study visit.
- w. NA treatment should be re-started in accordance with the NA re-treatment criteria (see Section [6.7](#), NA Re-treatment Criteria and Monitoring After Stopping of NA and Section [10.13](#), Appendix 13, for guidance after stopping NA treatment.

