- A post-treatment HBV DNA value of >20,000 IU/mL should trigger re-testing of ALT/AST, HBV DNA, and total and direct bilirubin within a maximum of 7 days from receipt of the data and further repeats as necessary (ie, weekly until HBV DNA returns to <20,000 IU/mL).
- A post-treatment HBV DNA value of >2,000 IU/mL (but <20,000 IU/mL) should trigger a re-test within 14 days from receipt of the data and further repeats as necessary (ie, every other week until HBV DNA returns to <2,000 IU/mL).
- A post-treatment ALT value of >5x ULN should trigger re-testing of ALT, AST, alkaline phosphatase (ALP), total and direct bilirubin, INR, albumin, and HBV DNA on a weekly basis until ALT and AST levels have returned to <5x ULN.

After stopping NA treatment, participants should restart NA treatment:

- Immediately with signs of decreasing liver function based on laboratory findings (eg, INR, direct bilirubin) or clinical assessment (eg, ascites, hepatic encephalopathy).
- Immediately with an HBV DNA value of >100,000 IU/mL (irrespective of confirmation and/or ALT increase).
- With confirmed post-treatment HBeAg seroreversion (HBeAg positive after it was negative at NA completion).
- With confirmed* post-treatment increases in HBV DNA >2,000 IU/mL and ALT >5x ULN.
- With confirmed* post-treatment increases in HBV DNA >20,000 IU/mL.

* At least 4 weeks apart – frequency of visits as described above.

Note: Additional re-testing and/or earlier restarting of NA treatment is at the investigator's discretion, even if the above cut-offs are not yet met.

To avoid delays in decision making, sites are encouraged to run local re-testing in parallel with central re-testing in the situations described above that require more frequent re-testing. Local test results are to be collected in the CRF and/or source documents, including information on the HBV DNA assay used. In addition, to avoid delays in NA re-treatment, it should be considered to dispense NA to participants who potentially met the NA re-treatment criteria (eg, pending confirmation) and who will not be available to come to the study site immediately at the time the confirmatory test results will become available. This should ensure that the participant can immediately restart NA treatment if indicated, upon direct confirmation by the investigator.

NUMBER OF PARTICIPANTS

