Peripheral blood mononuclear cell samples for immune analyses will be collected at selected sites at the time points indicated in the [Schedule of Activities](#) (see Section 8.7, Immune Assessments).

A pharmacogenomic blood sample will be collected from participants who consent separately to this component of the study (see Section 8.8).

Two PRO instruments (the HBV-specific self-stigma scale and EQ-5D-5L questionnaire) will be used to explore the impact of HBV treatment on participants (see Section 8.1.2, Patient-reported Outcomes).

Participants will be considered to have completed the study if they have completed the assessments of the end-of-study visit Follow-up Week 48 (Week 96).

If a participant discontinues study intervention before the end of the 48-week study intervention phase, follow-up assessments should be obtained until 48 weeks after EOSI unless the participant withdraws consent. NA treatment (either ETV, TDF or TAF as per local practice) should be continued at this time as per local treatment guidelines.

If a participant withdraws before completing the study intervention, the reason for withdrawal (if known) is to be documented in the case report form (CRF) and in the source document. Participants who withdraw consent will be offered an optional safety follow-up visit.

The [Schedule of Activities](#) summarizes the frequency and timing of efficacy, safety, and other assessments applicable to the Master Protocol PLATFORMPAHPB2001 and this ISA.

An IDMC will be commissioned for this study (Section 9.6, Independent Data Monitoring Committee). In addition, an IFLEP will be appointed (Section 9.7, Independent Flare Expert Panel).

A diagram of the study design is provided in Section 1.2, Schema.

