7. DISCONTINUATION OF STUDY INTERVENTION AND PARTICIPANT DISCONTINUATION/WITHDRAWAL

If a participant discontinues study intervention for any reason before Week 48, the participant will have an early withdrawal visit and will enter follow-up unless he/she withdraws consent. If the reason for withdrawal from the study is withdrawal of consent, then the participant will be offered an optional safety follow-up visit. Study intervention assigned to the participant who discontinued study intervention may not be assigned to another participant.

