7.1. Discontinuation of Study Intervention

JNJ-3989 and JNJ-6379 (or matching placebos) must be discontinued before Week 48 for all reasons listed in Section 7.1 of the Master Protocol PLATFORMPAHPB2001 and for all additional intervention-specific reasons. All the discontinuation criteria are listed below and the intervention-specific criteria are highlighted (colored fill). For the few criteria from the Master Protocol that are specified or more restricted in this ISA, the changes compared to the Master Protocol are also highlighted (colored fill). When JNJ-3989 or JNJ-6379 (or the matching placebos) are discontinued, NA treatment may be continued or, in consultation with the sponsor, discontinued based on investigator judgement.

The discontinuation criteria are:

- The investigator believes that for safety or tolerability reasons (eg, AE) it is in the best interest of the participant to discontinue JNJ-3989 and JNJ-6379 (or matching placebos).
- The participant becomes pregnant.
- The participant has a \geq grade 3 rash or allergic reaction.
- The participant has signs of hepatic decompensation (ie, clinical evidence of ascites, bleeding varices, or hepatic encephalopathy).
- The participant has a confirmed \geq grade 3 estimated glomerular filtration rate (eGFR) abnormality and a drop from baseline of >10 mL/min/1.73 m², considered at least possibly related to JNJ-3989 or JNJ-6379. Change of NA treatment should be considered according to the prescribing information.
- The participant has a QTcF prolongation (defined as a QTcF value of >500 ms, or an increase from baseline of >60 ms) at any given time point.
- The participant requires ≥ 7 days of treatment with any of the disallowed medications listed in Section 6.5 and does not intend to discontinue treatment with the disallowed medication.

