the participant should discontinue JNJ-3989 and JNJ-6379 (or their matching placebos) and should be monitored on a weekly basis or as per good clinical practice until ALT and/or AST levels have returned to <5x ULN and HBV DNA is <20,000 IU/mL and, if present, liver-related symptoms have improved. NA treatment should be continued. Additional tests can be considered based on clinical judgement.

The NA re-treatment criteria and monitoring after stopping of NA are presented in Section [6.7](#).

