8.3.6.5. Hematologic Abnormalities

Mild thrombocytopenia was observed in recently conducted non-clinical toxicology studies with the combination of JNJ-3989 and JNJ-6379. In addition, in a 3-month combination study with 80 rats, 1 rat developed pancytopenia related to bone marrow depletion after 23 days of dosing. Previously, in a 9-month dog study in 24 dogs treated with JNJ-6379 alone, pancytopenia which correlated with a marked increase in plasma cell-like cells in the bone marrow was observed in 1 dog after 60 days of dosing.

No thrombocytopenia or pancytopenia has been observed in the ongoing Jade study (56136379HPB2001) investigating JNJ-6379/Placebo with or without NA treatment. All 232 participants have completed at least 24 weeks of study treatment. In the Phase 1/2a AROHBV1001 study with JNJ-3989, mild transient thrombocytopenia (Grade 1) was observed in 6 out of 84 participants receiving 3 SC injections of JNJ-3989 alone over a period of up to 12 weeks with background of NAs. The transient thrombocytopenia was not considered clinically significant. No thrombocytopenia or pancytopenia was observed in 12 patients when JNJ-3989 and JNJ-6379 were given in combination over a 12-week period.

Based on the non-clinical findings, any relevant abnormalities in hematologic parameters will be carefully monitored as described below:

- Platelet counts: <100,000 cells/mm³ or <100 G/L or reduction from baseline by at least 50%
- Hemoglobin: Decrease of at least 2 g/dL from baseline or at least Grade 2 (DAIDS)
- Reticulocytes: Reduction to <0.5% of the RBC count
- Neutrophil count: Treatment emergent reduction to at least Grade 2 (DAIDS)

In case any one of the above criteria are met, a confirmatory visit should be scheduled as soon as possible, preferably within 7 days of the receipt of the initial results. Confirmation of the results will trigger weekly or biweekly (every other week) unscheduled visits until improvement or stabilization of the respective parameter(s). Stabilization is defined as no further significant reduction over two consecutive visits.

In case of confirmed Grade 3 or Grade 4 hematologic abnormalities, discontinuation of investigational study treatment (JNJ-3989 and/or JNJ-6379/placebo) should be considered. In case of discontinuation, NA treatment should be continued.

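### Footnote c of the follow-up schedule confines NA to two groups, while other current protocol text provides for NA in three further situations; the passages need reconciling

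*Protocol*

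**What the plan says.** Footnote c sits on the row of Protocol Section 1.3.2 that covers administering and dispensing NA at follow-up visits. It says that this "NA is only applicable for participants who could not stop NA treatment at Week 48, or for those who met the NA re-treatment criteria". Footnote k, in the Week 48/withdrawal column of the treatment-phase schedule (Section 1.3.1), names only participants who cannot stop NA at Week 48.

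The body of the protocol deals with NA in follow-up in several other places:

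- **Early discontinuation.** Section 7 says that after stopping study intervention before Week 48 "the participant will have an early withdrawal visit and will enter follow-up unless he/she withdraws consent". Section 4.1 says of these participants: "NA treatment (either ETV, TDF or TAF as per local practice) should be continued at this time as per local treatment guidelines". Section 8.3.6.3, on stopping the two investigational drugs for ALT/AST elevations, says "NA treatment should be continued". Section 8.3.6.5, on hematologic abnormalities, says "In case of discontinuation, NA treatment should be continued". Section 7.1 is looser: "NA treatment may be continued or, in consultation with the sponsor, discontinued based on investigator judgement".
- **Confirmation pending.** Sections 1.1, 4.2 and 6.7 say "it should be considered to dispense NA to participants who potentially met the NA re-treatment criteria (eg, pending confirmation"), provided that those participants cannot come to the site at once when the confirmatory results arrive.
- **Discretionary restart.** Sections 1.1, 4.2 and 6.7 and Appendix 13 allow restart before the listed cut-offs are reached. The synopsis wording is "Additional re-testing and/or earlier restarting of NA treatment is at the" investigator's discretion.

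**The concern.** The word *only* makes footnote c an exclusion rather than an incomplete list. The three situations above fall outside it, so the schedule and the text give different answers to the same practical question: may this participant be given study NA at this visit?

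Sites commonly work visit by visit from the schedule, and footnote c is attached to the row they would consult. If they follow it literally, study NA could be withheld or handed out late to a participant for whom the text provides it. The stated purpose of the advance-dispensing text is to prevent delay in re-treatment, so a narrower rule on the dispensing row works against it.

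**Working it through.** There is no figure to reproduce. The check is whether each situation fits either category in footnote c: (A) could not stop NA at Week 48, or (B) met the re-treatment criteria.

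| Situation in the text | Force of the text | Fits A? | Fits B? |
|---|---|---|---|
| Stopped study intervention before Week 48, in follow-up, NA continued (4.1, 8.3.6.3, 8.3.6.5; compare 7.1) | Directive in 4.1, 8.3.6.3 and 8.3.6.5; permissive in 7.1 | No: they left before Week 48 and never reached the Week 48 stopping decision | No: the criteria apply after NA has been stopped |
| Criteria potentially met, confirmation pending, cannot attend promptly (1.1, 4.2, 6.7) | To be considered | No: NA was stopped | No: not yet met |
| Restart at discretion before the cut-offs (1.1, 4.2, 6.7, Appendix 13) | Permissive | No: NA was stopped | No: by definition the cut-offs are not met |

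All three fall outside both categories as worded. The conflict is plainest in the second and third rows, where the text describes criteria that are not, or not yet, met and the footnote requires them to be met. For early discontinuers, category A could be stretched to mean anyone still on NA at that time, but the footnote ties it to Week 48.

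Footnote k does not fill the gap. Its column also serves the early-withdrawal visit, yet its wording covers only those who cannot stop at Week 48.

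Two further comparisons:

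- **Within Section 1.3.2.** The visit row for participants whose NA is not stopped or is restarted is limited neither to Week 48 nor to criteria having been met. The schedule is therefore narrower in its dispensing footnote than in its visit plan.
- **Against the SAP.** Section 5.3.2.1.4 cross-tabulates actual restart against criteria met or not met. The analysis plan thus allows for restarts without the criteria being met, which footnote c does not.

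The early-discontinuation text is itself uneven: Section 7.1 leaves NA to judgement where Sections 4.1, 8.3.6.3 and 8.3.6.5 say it continues. That also needs reconciling, and no view is taken here on which rule is right.

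**The case against.** The best defence is that a site reading the whole schedule is sent to the fuller text. Footnote i refers to Section 8.3.6.3, where continuation of NA after ALT/AST elevations is stated. Footnote w refers to Section 6.7 and Appendix 13, where the discretion note appears. The dispensing row is marked as applicable at every follow-up visit. Section 6.5 (Table 3) allows standard-of-care NA, and Section 4.1 itself refers to local practice. The most urgent triggers, declining liver function and HBV DNA above 100,000 IU/mL, call for immediate restart, and those participants have met the criteria, so footnote c covers them.

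Much of this stands, and it is why the consequence is stated as *could*. It does not dispose of the point. Footnotes i and w sit on laboratory rows, not on the dispensing row. Appendix 13 lacks the advance-dispensing text. Footnote c is what tells a site when the dispensing row applies, and none of these cross-references removes its *only*.

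A reader might also infer more than the documents support:

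- **That every participant awaiting confirmation is affected.** The text is limited to those who cannot attend promptly, asks only that dispensing be considered, and still requires the investigator's direct confirmation before restart.
- **That the footnote causes a wait of 4 weeks or more.** That interval comes from the confirmation rule and would be the same with a corrected footnote.
- **That participants stopped for liver injury would have no study NA.** Section 8.3.6.3 says NA continues, Section 6.1 says the sponsor provides it, and footnote i points to Section 8.3.6.3.
- **That advance dispensing was added because of the hepatic-failure case.** Section 2.3.3 links that case to the monitoring and re-treatment criteria and does not mention advance dispensing.
- **That footnote v adds a fourth contradicting group.** It is a specific provision for the end-of-study visit, refers to local standard of care, and says that sponsor supply ends after the final visit.

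**Conclusion.** The contradiction is real and lies in current text. Footnote c excludes three situations for which the protocol elsewhere provides NA in follow-up, and footnote k shares the gap for early discontinuers. The text is directive only for early discontinuers, and there only in some sections; for the other two situations it is permissive. The supportable consequence is that a site relying on the schedule could withhold or delay study NA.

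The size cannot be stated. The documents give no early-discontinuation rate, no expected number of discretionary restarts and no count of participants who could not attend promptly. The conclusion does not depend on any of these.

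Sample size, power and alpha are unaffected. The only link to the primary endpoint is how a restart is recorded. NA re-treatment between Weeks 48 and 72 makes a participant a non-responder (SAP Section 5.2.2), and SAP Section 5.3.1.1.8 identifies restarts from the study-drug administration page for the NAs. If a discretionary restart used NA from outside the study supply, it might not appear there; the documents do not say. Early discontinuers are non-responders already, so their continued NA does not change the primary result.

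**What to change.** Reconcile footnote c (Section 1.3.2) and footnote k (Section 1.3.1) with Sections 1.1/6.7, 4.1, 7.1 and 8.3.6.3, so that the schedule and the text carry the same list of participants who may be dispensed study NA in follow-up. The list should deal explicitly with early discontinuers, participants with confirmation pending who cannot attend promptly, and restarts at the investigator's discretion. The repeats in Sections 4.2 and 8.3.6.5 and Appendix 13 should be checked against it. Which participants belong on the list, and which of the differing statements on NA after early discontinuation holds, is for the sponsor to decide.

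The cost is a wording change in the next amendment or a letter to sites. It needs no extra visits, samples or staff, and no change to the analysis.
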